Examinations will be performed at a single USAF medical facility having dermatologic, neurologic and electromyogram/nerve conduction capabilities. Special Air Force authorization will be obtained to conduct such examinations on individuals separated from the service and informed consent forms will be obtained for nerve conduction tests. Physicians and technicians will handle

all participants without a knowledge of exposed or control status, and will conduct the examinations by standardized protocols to minimize variability. Medical students and interns will not perform these examinations, and specialty trained neurologists and dermatologists will perform the appropriate portions of the examination. An onsite monitor will insure that the examination protocol is followed. Clinical specimens will be forwarded to USAFSAM where most of the laboratory procedures will be conducted. The only laboratory procedures to be accomplished at the examining facility will be those which require immediate processing (see Section XIV, D(5)). All laboratory tests will thus be subject to the same technology and rigid quality control. Laboratory and physical examination data will be measured on a continuous scale whenever possible in order to improve statistical power in the analysis.

Special contingencies will be made for unusual laboratory testing. Karyotyping of the individual and his family members will be performed if clinical history or physical examination findings are suggestive of this need. Most well conducted studies have shown that, when present, chromosomal abnormalities due to TCDD are transient. If on detailed analysis of the baseline examination and questionnaire, reproductive areas are heavily affected, routine karyotyping may be included in the test battery for the follow-up study. TCDD analysis on blood and urine will be considered in the future provided that (1) strong cause and effect relationships can be ascribed to Herbicide Orange and (2) high resolution mass spectrometry technology achieves 10 femtogram sensitivity with high specificity. Appropriate specimens will be obtained from all participants, aliquoted, and preserved at -70°C for possible analysis in the future.

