Physical examination and laboratory data will be placed in the member's coded master file for detailed cross-analysis to questionnaire data. Information identifiable to the subject will not be released without his consent in accordance with the Privacy Act. (Exceptions: In accordance with Air Force regulations, all active duty flying personnel and air traffic controllers found to have disqualifying defects will be temporarily "grounded" pending resolution; in accordance with federal regulations, all commercial airline pilots and air traffic controllers found to have disqualifying defects will be reported to the Federal Aviation Administration.)

E. Follow-up Study

(1) Study Adaptations

Following complete data analysis of the mortality and morbidity studies, an adaptive or restrictive health survey will be developed and administered to all follow-up study subjects three and five years after the initial questionnaire. Similarly, a condensed physical examination profile that will achieve adequate sensitivity and specificity for prospective diagnosis will be

developed. The adaptive physical examination will be offered to all follow-up participants, and will also be conducted in years three and five (see Appendix, Table A-5). An interim examination is essential in this study because the age group under study is approaching that portion of the mortality/illness incidence curve with the steepest slope. A lapse of five years between examinations would easily miss significant development of disease in the intervening years. Ample precedent for interim examinations can be found in the Framingham cardiovascular disease study and the follow-up evaluation of West Point graduates being conducted by the Air Force.

(2) Entry Criteria

All exposed or control individuals completing the baseline questionnaire and physical examination will be entered into the follow-up; further continuation will depend upon the member's willingness/ability to participate in additional health surveys and condensed examinations.

[figure not shown]
(3) Loss to Study

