Loss of participants over time adversely affects any epidemiologic study in two ways. As the sizes of the study groups decrease, statistical power also declines, and bias is injected into the study if losses are not randomly distributed in the study populations. It is reasonable to assume that in this study, losses will be non-random with greater non-compliance among individuals who perceive their health as "well," since there is less incentive for this group to continue participation. As shown in Figure 3, such a differential pattern of loss will alter the population and skew the frequency distribution curve.

Most previous epidemiologic studies have approached the problem of declining statistical power by beginning the study with multiple controls per exposed subject, and passively allowing attrition to occur throughout the study period. However, this approach does not address the problem of bias. This study will take an active approach to both of these problems by using a replacement concept. As a control is lost to study, a replacement will be chosen from the original set of 10 matched controls. The replacement will be selected from the control set, and will have a perception of health similar to that of the lost control (Figure 4). The replacement strategy will maintain statistical power and the integrity of the matched design despite loss to study in the control group, and will correct anticipated bias while minimizing the number of required physical examinations.

[figure not shown]
At the initiation of the follow-up study, loss of an exposed member will not be cause to cease surveillance of his primary matched control. In the event of a control loss (for reasons other than death), another control from the set will be brought to study (Figure 5), the comprehensive questionnaire will be administered, and a baseline physical examination performed. Medical data

EFFECT OF NON-RANDOM LOSS TO STUDY IN THE CONTROL POPULATION

- IF CONTROL LOSSES ARE ILL, A SPURIOUS EFFECT IS ATTRIBUTED TO HERBICIDE EXPOSURE.
- IF CONTROL LOSSES ARE WELL, A TRUE/VALID HEALTH EFFECT IS DILUTED.

ANALYSIS OF THE REPLACEMENT STRATEGY

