The USAF is committed to expending maximal effort to encourage participation. Loss to study problems in the study participants will be avoided as much as possible by detailed and exhaustive efforts to contact and followup each identified participant. NON-PARTICIPANTS WILL BE STRONGLY ENCOURAGED TO RECONSIDER THEIR INITIAL DECISIONS. Design considerations have been made to minimize loss to study in both the exposed and control populations. Although the USAF can not compensate study subjects for lost wages during the physical examination, transportation costs, per diem, and lodging costs will be reimbursed.

The replacement concept will help to counteract the decrement in statistical power, and offset the bias created by differential patterns of loss. The exposed group is already of maximum size and cannot be increased, but non-compliant controls can be replaced. This will maximize the degree of pairing between the two study groups. If a non-compliant control is replaced by a control with a similar perception of his own state of health, the alteration of the control group distribution is offset; (i.e., an "ill" control is replaced with an "ill" individual, and a "well" control with another "well" individual.) This concept of replacement, coupled with extensive efforts to encourage compliance will minimize losses to study and offset the adverse effects of those losses that do occur.

H. Statistical Power Limitations

(1) Problem

As discussed above, statistical power considerations are heavily dependent on loss to study rates. Since the design of the study is also limited by the small exposed population, statistical power for identifying the relative risk of an uncommon disease or symptom-complex ($<1/100$) is very low ($<.50$), (See Section VI F). This study will, to a greater extent, be able to detect increased risks only in common diseases or symptom-complexes ($>1/100$).

(2) Discussion

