Variability in examination procedures will be minimized by the use of standardized procedures, examination protocols, similar equipment, and training. Most laboratory procedures will be conducted centrally at the USAFSAM, and quality control will be stressed at all times. Where at all possible, the same physician/technician teams will be used for each study phase.

J. Confounding Exposure Factors

(1) Problem

While virtually all of the media attention has been directed toward the 2,4,5-T-containing herbicide formulations, other herbicides were applied concurrently by the C-123 aircrews in Vietnam. Herbicide Blue (Cacodylic acid with 15.4% pentavalent arsenic) and Herbicide White (2,4-D and Picloram) were used throughout the 1962-1970 time period. Any long-term health effects from these

additional compounds may confound the results of the study. Peripheral neuritis, tremors, skin and lung cancer, loss of hair and nails, skin rashes, and gastric symptoms have been alleged after exposure to arsenical pesticides. The organophosphate insecticide, Malathion, was also sprayed by many of these same aircrewmembers when RANCH HAND duties permitted their temporary assignment to mosquito/malaria control units. Many of these individuals were involved in the aerial spray application of these and other pesticides both before, during, and after their Vietnam service. Long-term effects from these chemicals would confound the study results.

The small size of the RANCH HAND population will allow very little opportunity for analytic stratification for these confounding variables. Differing patterns of exposure to aircraft fuels in the study populations have been suggested as confounding factors. The C-130 aircraft were powered by turbo-prop engines which used jet fuel (JP-4), while the C-123 and C-7 aircraft were powered by standard reciprocating engines which used leaded aviation fuel (AV-GAS). After June 1968, many C-123s were modified by the addition of auxiliary jet engine boosters for added power on takeoffs and emergencies.

(2) Discussion and Corrective Measures

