A review of systems will be attempted, specifically emphasizing the neurologic, dermatologic, reproductive, and hepatic systems as well as specific symptoms associated with a neoplastic condition.

Specific questions will address the personality makeup of the individual in order to assess his potential risk-taking behavior (see Section VIII.C). Information verification and bias indicator questions will also be integrated into the questionnaire.

During this initial telephone questionnaire, those participants agreeing to undergo a physical examination will be instructed to insure that the medical examiners are "blind" as to whether or not they were former RANCH HAND personnel.

At the time of physical examination(s), the subject will receive a comprehensive face-to-face questionnaire which will expand and verify the information that was obtained in the telephone questionnaire and records review. An extensive review of systems will be covered at that time, including a more extensive occupational and avocational exposure history.

Just prior to the time of follow-up physical examinations (FY 1982 and FY 1984), a preliminary telephone contact will establish the subject's current health status and his willingness to continue participation in the study. An appointment for the followup examination will also be arranged. An adaptive telephone questionnaire will be given emphasizing those symptoms and systems that were found to be significantly associated with the exposed population on statistical analysis of the first year's results. If the subject expresses a desire to cease participation at this time, he will be encouraged to reconsider his decision and reasons for dropping out of the study will be sought.

XIV. Physical Examination Design

A. General Comments

This phase of Project RANCH HAND II is a cross sectional study of the subject's health at the time of examination. It is important that examiners remain unaware of the subject's status as a RANCH HAND participant or as a control subject. The physician examiner is tasked to examine and objectively record his findings. The examining physician is not, and cannot be expected to arrive at any definitive diagnosis as the full history and laboratory results are not available to him. The compilation and analysis of data will be performed by the study investigators at Brooks Air Force Base, Texas. They will notify the subject and the physician of his choice of the results of the examination.

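### A replacement control entering at year 3 or 5 gets the full baseline battery while continuing men of both groups get the condensed one, so the battery can reveal control status for part of the control group

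*Protocol*

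**What the plan says.** For follow-up, protocol section V.E(1) states that "a condensed physical examination profile that will achieve adequate sensitivity and specificity for prospective diagnosis will be" developed, and that "The adaptive physical examination will be offered to all follow-up participants, and will also be conducted in years three and five". An adaptive survey goes to the same men. Section V.E(2) sets the entry rule: "All exposed or control individuals completing the baseline questionnaire and physical examination will be entered into the follow-up".

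Section V.E(3) treats a control lost for reasons other than death differently: "another control from the set will be brought to study (Figure 5), the comprehensive questionnaire will be administered, and a baseline physical examination performed". Section VIII.G(2) explains why this applies to one group only: "The exposed group is already of maximum size and cannot be increased, but non-compliant controls can be replaced".

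On masking, section V.D(4) says that physicians and technicians will handle "all participants without a knowledge of exposed or control status", and section XIV.A says: "It is important that examiners remain unaware of the subject's status as a RANCH HAND participant or as a control subject". Examinations take place at a single facility (V.D(4)), and section VIII.I(2) adds: "Where at all possible, the same physician/technician teams will be used for each study phase".

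Sections VI.A and VI.I require replacements to be flagged and compared with the controls they replace. Intact pairs are analysed first, and all pairs, including those with replaced controls, are analysed in addition.

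**The concern.** Each rule is reasonable alone. Together they tie the length of the battery to group membership at years 3 and 5: a man on the condensed battery may belong to either group, while a man on the baseline battery is, under the rules as written, a replacement control.

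Two things are at stake. The first is masking. Section VIII.D names false positive response as the main expected bias and relies on the standardized examination as the main correction for it. If the battery discloses status, that correction is weakened, and in one group only. The second is unequal examination within the round: a longer battery offers more opportunities to record an abnormality. Either could move the finding rate in controls for reasons unrelated to herbicide.

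**Working it through.** **Who can be on which battery at years 3 and 5**

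- Continuing exposed man: condensed (V.E(1)). He had the full battery at baseline (V.E(2)).
- Continuing control: condensed, likewise after a full baseline.
- New replacement control: comprehensive questionnaire and baseline examination (V.E(3)).
- New exposed man: no provision. The contact schedule in the Appendix (Table A-5 in the list of tables) places the baseline examination in March 1980 to March 1981 only.

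Replacements do arise at these rounds. Section XIII has willingness to continue checked just before each follow-up examination, and Table 14 counts controls by examination number, including examinations 2 and 3. Nothing in the document conceals the type of battery from the examiner. The instruction to participants in section XIII to keep examiners blind does not cover it.

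**How many controls are affected**

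Inputs, from section VI.I and Tables 14 and A-6: 1000 matched sets, 10 controls per set, P1 = .70 (refusal when first asked) and P2 = .25 (loss of a man already examined).

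The plan's own figure first. The Table 14 columns sum to 967, 936 and 912 attending, with 33, 64 and 88 failures, so each column totals 1000. The first expectation can be checked by hand: 1000 × (1 − .70^10) = 1000 × (1 − .028) = 972. Re-running the program of Table A-6 gives expected attendance of 972, 942 and 905, each within 1% of Table 14. Expected failures are 28, 58 and 95. Table 14's failures lie inside the 95% simulation ranges for a single run of 1000 (18–39, 45–72, 78–115). Table 14 is reproduced.

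First-time attendees at examination j = attending at j − (1 − P2) × attending at j − 1.

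- Examination 2: 936 − .75 × 967 = 211, and 211/936 = 22.5%.
- Examination 3: 912 − .75 × 936 = 210, and 210/912 = 23.0%.

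Counting first attendances directly in the re-run gives 213 of 942 (22.6%) and 198 of 905 (21.9%).

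**Sensitivity to P2, with P1 held at .70**

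| P2 | Share new, exam 2 | Share new, exam 3 |
|---|---|---|
| .05 | 4.4% | 4.5% |
| .10 | 8.9% | 8.9% |
| .15 | 13.4% | 13.1% |
| .25 | 22.6% | 21.9% |
| .35 | 32.1% | 31.1% |

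The counts are per 1000 sets and are not forecasts, since section V.D(2) expects only about 40% of exposed men to be examined. The share is the relevant quantity.

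**The case against.** Several points on the other side are sound and limit the finding.

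- A reader might infer that exposed men are examined only with the condensed battery throughout. They are not: entry to follow-up requires a completed baseline, so every continuing exposed man has had the full battery once. The inequality exists only within a follow-up round.
- A reader might infer that the blind fails between the groups as a whole. It does not. Continuing controls and exposed men share the condensed battery and stay masked from each other. Replacements made during the baseline phase are also unaffected.
- A full baseline at year 3 or 5 is not absolute proof of control status. Section VIII.G(2) has non-participants encouraged to reconsider, so a late first examination of an exposed man is not expressly excluded. None is provided for, however.
- Recognition is an inference. It needs an examiner who sees the difference and knows the replacement rule. The baseline questionnaire is by telephone, and the condensed profile is not yet written. One facility and stable teams make recognition plausible, not certain. Telephone interviews are also to be blind as far as possible (VIII.D(3)), so the questionnaire raises the same issue for interviewers.
- Whether the review of systems would differ is unsettled. Section XIII places the comprehensive face-to-face interview at the physical examination(s), while the contact schedule lists it only at baseline.
- Analysing intact pairs first, with replacements flagged, does protect that analysis. Flagging does not restore masking in the all-pairs analysis, which is the one the replacement scheme exists to serve.

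**Conclusion.** The point stands in limited form. As written, the rules let the battery reveal control status for replacement controls entering at years 3 and 5, contrary to V.D(4) and XIV.A. Within that round, those controls are examined more extensively than the exposed men they are compared with. The all-pairs analysis is exposed to this; the intact-pairs analysis is not.

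The size is about 22–23% of examined controls at each follow-up round under P1 = .70 and P2 = .25, and about 4% to 32% for P2 from .05 to .35. Section VI.I folds mortality into P2, yet dead controls are not replaced (V.E(3), VI.I), so the share is somewhat overstated, by an amount that the document does not allow one to compute.

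It would be tempting to read 22–23% as a bias. It is only the fraction of controls in whom masking and examination intensity could differ. The document gives no basis for the size or direction of any resulting shift in finding rates. The case for change rests on the differential nature of the problem and the low cost of removing it.

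**What to change.** Reconcile V.D(4), V.E(1), V.E(3) and XIV.A as follows.

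1. At years 3 and 5, every attendee, new or continuing, first receives the identical condensed questionnaire and examination.
2. That record is closed before the examiner learns of, or performs, any added baseline items for a new entrant.
3. The year-3 and year-5 all-pairs comparisons use only the condensed items common to everyone.
4. Late entrants' extra items serve only to describe them and to compare them with the controls they replaced.

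The cost is a re-ordered and slightly longer visit for replacements, one added sentence on the analysis, and no use of their extra items in the group comparison. The baseline data on replacements are still collected.
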